5.10 Data Collection, Management and Analysis

5.10.1 Data Collection Methods

Data will be collected at the time-points indicated in the Participant Timeline (Section 5.6).

The research team will complete paper CRFs for questionnaires and assessments which take place during face to face visits. Standard care information should be recorded in patient notes. These data must then be entered onto a central database via an online system, access and training will be provided by NCTU. Identification logs, screening logs and enrolment logs will be kept locally, either in paper or electronic form. Patient questionnaires may be completed online if face-to-face or postal completion are unfeasible.

Source data worksheets will be drafted by the data manager with the CIs, trial statistician and PIs. These will be piloted and finalised. The database specification will be prepared by the NCTU data manager and approved by the CIs and trial statistician prior to the database being built. The database will be prepared by the NCTU Data Management Team and tested by the trial team and study site staff for user acceptability prior to the final system being launched.

Data collection, data entry and queries raised by a member of the PREPARE-ABC trial team will be conducted in line with NCTU and trial specific Data Management Standard Operating Procedures.

Clinical trial team members will receive trial protocol training. All data will be handled in accordance with the Data Protection Act 1998 and GDPR (2018).

5.10.2 Data Management

Data will be entered in the approved PREPARE-ABC database by a member of the site staff identified on the delegation log.

Participants will be given a unique trial Participant Identification Number (PIN). Data will be entered under this identification number onto the central database stored on the servers based at NCTU. The database will be password protected and only accessible to members of the PREPARE-ABC trial team at NCTU. The servers are protected by firewalls and are patched and maintained according to best practice. The physical location of the servers is protected by CCTV and security door access.

The database and coding frames have been developed by the Clinical Trial Manager in conjunction with NCTU. The database software provides a number of features to help maintain data quality, including; maintaining an audit trail, allowing custom validations on all data, allowing users to raise data query requests, and search facilities to identify validation failure/ missing data. Further details can be found in the PREPARE-ABC Data Management Plan.

After completion of the trial the database will be retained on the servers of NCTU for on-going analysis of secondary outcomes.

The identification, screening and enrolment logs, linking participant identifiable data to the pseudo-anonymised Participant Identification Number, will be held locally by the trial site. This will either be held in written form in a locked filing cabinet or electronically in password protected form on hospital computers. After completion of the trial the identification, screening and enrolment logs will be stored securely by the sites for 10 years unless otherwise advised by NCTU.

5.10.3 Non-Adherence and Non-Retention

The consent form will explain that if a participant wishes to withdraw from the study the data acquired prior to that point will be retained, unless the patient requests otherwise. Reason for withdrawal will be recorded, if given, as will loss to follow up.

Non-adherence to trial exercise procedures will be assessed by the Trial Intervention team and recorded in the eCRF.

5.10.4 Statistical Methods

5.10.4.1 Statistical Analysis Plan

A full Statistical Analysis Plan (SAP), and interim analysis plan(s) as required, will be developed between the trial statistician and Chief Investigators and agreed with the trial's governance committees.

IRAS No: 200804

5.10.4.2 Statistical Methods - Outcomes

Primary outcomes

- Total SF-36 score at 12 months post-randomisation; and
- The presence or absence of any morbidity at 30 days post-operation.

Secondary efficacy

- pre-operative outcomes: Cardiopulmonary exercise testing (CPET) variables; Grip strength
- post-operative outcomes: Length of hospital stay as measured from date of operation, time
 until fitness for discharge from date of operation, 90-day all cause re-admission rate from date
 of operation, 90 day post-operative mortality from date of operation, grip strength
- psychological health status: Hospital Anxiety and Depression Scale (HADS) at 6 and 12 months post-randomisation.
- Physical activity behaviour using the Godin Leisure time exercise questionnaire at 6 and 12 months
- EQ-5D-5L at 30 days post-operative, 6 and 12 months post-randomisation
- SF-36 at 30 days post-operative and 6 months post-randomisation
- SF-36 subscales, mental and physical health, at 6 and 12 months post-randomisation
- Self-efficacy and motivation for exercise using Self Efficacy for Exercise Scale, Behavioural Regulation in Exercise Questionnaire and Exercise Identity scale

5.10.4.3 Additional Analyses - Subgroup

No subgroup analyses are planned.

5.10.4.4 Additional Analyses

In addition to the efficacy analyses, analyses will be undertaken which will attempt to correlate the changes in outcomes with the changes in CPET and grip strength variables using multivariable regression models. Additionally, with the different exercise groups we will attempt to correlate the changes in outcomes with the adherence within the groups.

5.10.4.5 Analysis Population and Missing Data

The analyses population are defined as:

- a) intention-to-treat: all randomised individuals regardless of adherence;
- b) per-protocol: all randomised individuals who adhere to the study regime attending at least 50% of the hospital supervised exercise sessions or participate in at least 50% of scheduled phone calls with a member of the trial intervention team relative to the treatment arm they are allocated to.
- c) safety population:
 - Arm A all randomised individuals who receive a manual and attended a minimum of one supervised exercise session
 - Arm B all randomised individuals who receive a manual
 - Arm C all randomised individuals

Missing data that occur in outcomes will be multiply imputed to increase precision of the treatment effect estimates. Sensitivity analyses will be conducted to assess the impact of the multiple imputations and a complete case analysis will also be conducted. All imputations will be examined to ensure sensible values are being generated. Imputation models will contain baseline measures, outcome measures and factors predictive of missing data.

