5.6.1.7 Surgery

Surgery and after care to follow treatment as usual, with no further study interventions until 6 weeks post-surgery. All POMs and length of hospital stay to be recorded in patient notes and ultimately captured in the eCRF.

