5.6.1.8 Post-surgery discharge

POM Clavien-Dindo Classification to be recorded from surgery completion to point of discharge. Fitness for discharge to be assessed by clinical team blinded to treatment intervention.

5.6.1.9 30 day post-surgery visit

30 day post-operative morbidity (Clavien-Dindo Classification) to be recorded from review of patient notes, from the date of discharge to the 30 days post-surgery, SF-36 and EQ-5D-5L questionnaires to be completed and grip strength (measured using a standard digital grip strength dynamometer) recorded. This visit may take within -3 days and +7 days of the schedule.

Post-operative morbidities re-experienced or worsened from the post-surgery inpatient stay should be re-recorded at the 30 day time point. Otherwise the recording of post-operative complications should not be duplicated.

5.6.1.10 6 week post-surgery to 12 month post-randomisation treatment phase

If a patient's return to exercise/usual activities is delayed due to post-operative complications, they may continue in the study and re-commence the exercise intervention once they are able. The protocol treatment interruption should be noted in the eCRF.

Participants randomised to Arm A will receive:

Information on the location of local exercise facilities and physical activity schemes in their local communities. Patients will be encouraged to comply with current physical activity recommendations of completing 150 minutes of moderate intensity aerobic exercise per week (e.g. brisk walking, cycling etc.), measured at 13-15 on the Borg RPE Scale (Borg 1970), and two sessions of resistance exercise per week.

Patients will also be offered supervised "booster" exercise sessions, approximately monthly until 12 months post-randomisation.

Each session will comprise 6 x 5 minute repetitions at 60-80% of heart rate reserve ($^{\circ}$ 60-80% peak VO₂; Borg RPE Scale 13-15 (Borg 1970) with 2.5 minute rest intervals. There will also be 2 home-based resistance exercise sessions per week.

These sessions will be delivered by a member of the Trial Intervention Team who has had trial specific training to deliver these interventions consistently to all Arm A participants.

Adherence to the exercise programme will be recorded in the eCRF from pedometer data, patient participation/attendance and patient completed exercise diaries. All exercise intervention AEs will continue to be recorded.

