5.7 Sample Size

An overall sample of 1146 patients (randomised 1:1:1) provides 90% power.

Post-operative complications are evident in 55% of patients by day 30 in patients receiving standard care. To detect a 25% reduction (relative risk 0.75) between standard care and each of the exercise groups (90% power, alpha 2.5%) 343 patients are required in each arm, giving 1029, 10% attrition rate - Total 1146. Average SF 36 score at 1 year is 52 SD 10.To detect a 3 unit difference between standard

care and each of the exercise groups (90% Power, alpha 2.5%) requires 276 in each arm, 3 arms 828, 20% attrition rate. Total 1035.

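### The per-protocol rule has no time window, so if it is used for 30-day morbidity, membership can depend on that outcome, chiefly in Arm B

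*Protocol*

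**What the plan says.** Section 5.10.4.5 sets out three analysis populations. Intention-to-treat is everyone randomised, whatever their adherence. Per-protocol is "all randomised individuals who adhere to the study regime attending at least 50% of the hospital supervised exercise sessions" or those who "participate in at least 50% of scheduled phone calls with a member of the trial intervention team", applied according to allocated arm. There is one definition for the whole trial, with no counting period, no version by outcome, and no condition that an Arm C patient could fail.

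The timing comes from other sections. Section 5.6.1.7 has surgery and after-care proceed "with no further study interventions until 6 weeks post-surgery". From then until 12 months after randomisation, Arm A is offered supervised boosters about monthly and Arm B a monthly call (section 5.6.1.10). That section also provides for the case where a patient's "return to exercise/usual activities is delayed due to post-operative complications, they may continue in the study" and restart later. One of the two primary outcomes is the presence or absence of any morbidity at 30 days after operation (section 5.10.4.2).

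**The concern.** Every post-operative session or call takes place after the 30-day outcome has been settled. A rule that counts those contacts classifies patients partly on events that follow the outcome and may be caused by it.

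In Arm B, a patient who takes all four pre-operative calls and then misses the later ones scores 4/13 = 31% and is excluded. A patient who takes none before surgery and seven of nine afterwards scores 7/13 = 54% and is included. For a 30-day outcome that is the wrong way round, since only exercise before surgery could have influenced it.

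Controls are not filtered. If complications reduce later attendance, complicated patients drop out of the exercise arms but stay in Arm C, and the comparison is biased towards exercise. At stake is a favourable per-protocol figure for a primary outcome, set beside the intention-to-treat result. Arm B matters particularly because section 5.12 makes B versus C the only comparison recruiting while Arm A is suspended.

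**Working it through.** **1. The plan's own figure.** Section 5.7 takes 55% complications under standard care and a relative risk of 0.75, so 0.55 × 0.75 = 41.25%, with "90% power, alpha 2.5%) 343 patients are required in each arm". A two-proportion formula at two-sided 2.5% gives 326 per arm, or 340 with continuity correction, close to 343. Then 343/0.90 = 381.1, rounded up to 382, and 382 × 3 = 1146, as stated. The 55% and the 343 are used below.

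**2. Contacts before and after the outcome.** Pre-operative contacts come from section 5.6.1.5: three sessions a week (Arm A) or one call a week (Arm B) for 3-4 weeks. Post-operative counts are an assumption: surgery at about week 4 and monthly contacts from about week 10 to week 52, so about 9. With a three-week lead, about 10 are assumed.

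| Arm | Pre-operative | Post-operative | Total | Needed for 50% | Largest pre-operative share |
|---|---|---|---|---|---|
| A, 4 weeks | 12 | 9 | 21 | 11 | 57% |
| A, 3 weeks | 9 | 10 | 19 | 10 | 47% |
| B, 4 weeks | 4 | 9 | 13 | 7 | 31% |
| B, 3 weeks | 3 | 10 | 13 | 7 | 23% |

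No Arm B patient can qualify on pre-operative calls alone. In Arm A with a four-week lead, 11 or 12 of 12 sessions already qualify.

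**3. Bias under no true effect.** Let a1 and a0 be the shares kept in the set with and without a complication. The complication rate in the set is r = 0.55·a1 / (0.55·a1 + 0.45·a0), and the relative risk against unfiltered controls is r/0.55. If a1 = a0, this is 1.00 exactly. It reaches the design value of 0.75 when a1/a0 = (0.4125/0.5875) ÷ (0.55/0.45) = 0.57.

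**4. Plausible values of a0 and a1.** The protocol gives no attendance by complication status, so these are assumptions. Post-operative attendance averages 70% without and 50% with a complication. Attendance counts in each period are beta-binomial with within-patient correlation 0.2, the two periods are independent, and complications are independent of pre-operative attendance. Four-week schedule:

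| Arm | Pre-operative attendance | a0 | a1 | r | Relative risk |
|---|---|---|---|---|---|
| B | 60% | 0.801 | 0.553 | 45.8% | 0.83 |
| B | 70% | 0.838 | 0.606 | 46.9% | 0.85 |
| B | 90% | 0.903 | 0.712 | 49.1% | 0.89 |
| A | 60% | 0.781 | 0.626 | 49.5% | 0.90 |
| A | 70% | 0.866 | 0.745 | 51.2% | 0.93 |
| A | 90% | 0.974 | 0.938 | 54.1% | 0.98 |

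The three-week schedule gives 0.82-0.86 in Arm B and 0.87-0.96 in Arm A.

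**5. How far the size moves.** With a smaller gap (70% versus 60%) and 70-90% pre-operative attendance, the four-week relative risk is about 0.94-0.95 in Arm B and 0.97-0.99 in Arm A. With larger gaps at 60% pre-operative attendance (60% versus 40%, then 60% versus 30%), it is about 0.77 and 0.6 in Arm B, and 0.88 and 0.80 in Arm A.

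**6. False positives.** For the 70% versus 50% case, a simulation over both schedules with 70-90% pre-operative attendance, tested against 343 controls, gave rates of 22-45% in Arm B and 3-18% in Arm A, against a nominal 2.5%.

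**7. Pre-operative contacts only.** The same simulation kept r at 55.0% with false-positive rates of 2.3-2.7%. This follows by construction from the assumed independence of pre-operative attendance and complications.

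**The case against.** The strongest reply has four parts.

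- **No assigned use.** No sentence assigns the per-protocol set to 30-day morbidity. The efficacy section (5.10.4.6) does not mention it, and where it deals with non-adherence it proposes CACE. This stands: a reader might infer that the trial's primary result is distorted, and the document does not support that. Equally, nothing confines the set to 12-month outcomes.
- **The window is unstated.** For Arm A a pre-operative reading is possible: half of 12 is 6, the minimum used in the pilot criterion (section 4.3.1). The number of calls counted as scheduled might also shrink for a patient who restarts late. A statistical analysis plan, not at hand, could settle this. But the pilot criterion separates pre-operative sessions from boosters and the per-protocol rule does not, and nothing in the call criterion limits it to the weeks before surgery.
- **The attendance drop is not documented.** Section 5.6.1.10 is conditional and lets patients restart. The outcome is any morbidity, including minor Clavien-Dindo grade I events, and a patient not yet exercising can still take a 15-minute call. This stands too. A reader might infer that complicated patients are in fact removed and that the result will favour exercise; the document supports only that this can happen.
- **Filtered exercisers against unfiltered controls is common to per-protocol analyses with an untreated arm.** True, and the fix does not remove it. What is specific here is that the filter uses contacts made after the outcome.

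**Conclusion.** The point holds as a conditional one. If the per-protocol set as written is applied to 30-day morbidity, membership can depend on the outcome. In Arm B this cannot be avoided under the assumed schedule; in Arm A it is weaker and nearly vanishes when pre-operative attendance is high.

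If complications lower later attendance, the bias favours exercise. With no true effect, 70% versus 50% post-operative attendance and 60-90% pre-operative attendance, the four-week schedule gives a relative risk of about 0.83-0.89 in Arm B and 0.90-0.98 in Arm A, against a design target of 0.75. With equal attendance there is no bias. These sizes rest on assumed attendance and an assumed contact schedule. The intention-to-treat result is not affected. The objection is weaker for SF-36 at 12 months, because most contacts precede that outcome.

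**What to change.** Define the per-protocol set by outcome. For 30-day morbidity and other peri-operative outcomes, require at least 50% of the sessions (Arm A) or calls (Arm B) scheduled before surgery. Keep full-period adherence for 12-month outcomes. Use the same pre-operative definition for adherence in any CACE analysis of a peri-operative outcome.

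This removes selection driven by the outcome. It does not remove confounding: frailer patients may both attend less before surgery and have more complications. The per-protocol result should therefore be labelled supportive, with CACE preferred because it keeps the randomised comparison.

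The cost is wording only. Session attendance and calls are already recorded in the eCRF (sections 5.4.4 and 5.10.5).

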5.10.4.6 Efficacy Analyses

The group comparisons which will be made are: a) TAU vs Hospital Based Supervised Exercise; b) TAU vs Home Based Supported Exercise; and c) Hospital Based Supervised Exercise vs Home Based Supported Exercise. The comparison a) and b) are the primary comparison and c) is an exploratory comparison as it is not possible to adequately power this comparison. No adjustment is made for multiple testing due to the number of groups as we are treating the comparisons a) and b) as separate research questions so we do not need to control the type 1 error/false positive rate.

For all 3 comparisons with the primary outcomes we will have a significance level of 2.5% to account for having two primary outcomes, this is based on the Bonferroni adjustment of dividing the significance level by the number of comparisons made for each research question. For all secondary outcomes the significance level will be 5%.

Within each group comparison for all continuous outcomes, a general linear model will be used to compare the average values between groups adjusted for the site as the randomisation is stratified by site. Depending on the number of individuals recruited at each site, site will be included as either a fixed or random effect. Assumptions will be checked graphically and if appropriate transformations will be used, if none are appropriate then a Bootstrap will be used. For binary outcomes a logistic regression model will be used adjusting for site.

In addition to the above analysis if any factor is imbalanced at baseline or is considered prognostic by discussion with the PI/TMG/DMC they will be included in an adjusted model. However, the primary analysis is the unadjusted analysis and the adjusted analysis exploratory.

If appropriate, that is to say that there is a large amount of non-adherers to the intervention, then a Complier Average Causal Effect (CACE) analysis will also be undertaken.

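### The fixed 2.5% split between the two primary outcomes is valid, but Holm's step-down test keeps the same 5% error per comparison and is never less powerful

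*Protocol*

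**What the plan says.** Protocol 5.10.4.6 names three comparisons: a) usual care against hospital exercise, b) usual care against home exercise, and c) the two exercise arms, which is exploratory. Within each of them, "we will have a significance level of 2.5% to account for having two primary outcomes". The stated basis is that "this is based on the Bonferroni adjustment of dividing the significance level by the number of comparisons made for each research question". Between comparisons a) and b) nothing is split: "No adjustment is made for multiple testing due to the number of groups", because they are treated as separate research questions. The error rate being protected is therefore 5% per comparison, spread over two outcomes. No step-down or recycling of alpha is mentioned.

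Protocol 5.7 sizes each outcome separately at 90% power and 2.5%. For morbidity, "343 patients are required in each arm, giving 1029, 10% attrition rate - Total 1146"; for SF-36, the calculation "requires 276 in each arm, 3 arms 828, 20% attrition rate. Total 1035". Section 4.2 words each primary hypothesis as a benefit on complications together with a benefit on quality of life. Section 5.11.2 plans no efficacy interim analysis.

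**The concern.** Under a fixed split each outcome faces the 2.5% threshold whatever the other one shows. Suppose morbidity gives p = 0.001 and SF-36 gives p = 0.03 in the same comparison. The plan must call SF-36 not significant, although a valid procedure at the same 5% familywise error would declare it. Once one of two null hypotheses is rejected at 2.5%, only one is left, and it can be tested at the full 5% without exceeding the familywise rate. The fixed split leaves that alpha unused.

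This matters most for showing benefit on both outcomes, which is how section 4.2 words each hypothesis. The price is a lower chance of that result than the same patients and the same error rate could give.

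**Working it through.** **Inputs from the protocol**
- Control complication rate (5.7): "Post-operative complications are evident in 55% of patients by day 30 in patients receiving standard care". With relative risk 0.75 the exercise rate is 0.55 × 0.75 = 41.25%.
- SF-36 (5.7): "Average SF 36 score at 1 year is 52 SD 10", difference 3 units.
- Attrition (5.7, 5.8.2): 10% for morbidity, 20% for SF-36.
- Assumption: 1146 randomised 1:1:1, that is 382 per arm.
- Assumption: two-sided tests. Sidedness is not stated, but 276 per arm reproduces only two-sided; one-sided gives 234.
- Assumption: the correlation of the two test statistics is not given. It is taken as 0, with a range to 0.8.

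**Reproducing the sample size**
- SF-36: n = 2(z₀.₉₈₇₅ + z₀.₉₀)² SD²/Δ² = 2(2.241 + 1.282)² × 100/9 = 275.8, so 276 per arm. 828/0.8 = 1035. Both match.
- Morbidity: the two-proportion formula gives 326 per arm without and 340 with continuity correction. The stated 343 is close to the latter. 343/0.9 gives 382 per arm, and 3 × 382 = 1146, as stated.

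**Power for each outcome at the recruited size**
- Morbidity, 343 evaluable per arm: Φ[(|p₁ − p₂|√n − z√(2p̄q̄))/√(p₁q₁ + p₂q₂)].
  - At 2.5%: Φ[(2.547 − 1.584)/0.700] = 91.6%.
  - At 5%: Φ[(2.547 − 1.385)/0.700] = 95.2%.
- SF-36, 382 × 0.8 = about 305 evaluable per arm: Φ[3/(10√(2/305)) − z].
  - At 2.5%: Φ(3.705 − 2.241) = 92.8%.
  - At 5%: Φ(3.705 − 1.960) = 95.9%.

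**Confirming both outcomes in one comparison, independent outcomes**
- Bonferroni, both p ≤ 0.025: 0.9155 × 0.9283 = 85.0%.
- Holm, both p ≤ 0.05 and at least one p ≤ 0.025: 0.9155 × 0.9595 + 0.9515 × 0.9283 − 0.8499 = 91.2%.
- A simulation of the same case gave 84.6% and 91.2%.

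**Each outcome under Holm**
- Morbidity: 0.9155 + 0.9283 × (0.9515 − 0.9155) = 94.9%, up 3.3 points.
- SF-36: 0.9283 + 0.9155 × (0.9595 − 0.9283) = 95.7%, up 2.9 points.
- At least one success: 1 − 0.0845 × 0.0717 = 99.4% under either rule, because Holm's first step is the Bonferroni test.

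**Sensitivity of the chance of confirming both**

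| Case | Bonferroni | Holm |
|---|---|---|
| Correlation 0.3 | 85.8% | 91.5% |
| Correlation 0.5 | 86.7% | 91.8% |
| Correlation 0.8 | 88.6% | 92.7% |
| Continuity-corrected morbidity power, independent | about 84% | about 90% |
| Only 276 per arm for SF-36, independent | 82.4% | 89.4% |
| Exactly 90% power for each, independent | 81.0% | 88.4% |

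The gain is about 4 to 7 points throughout.

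**Error rate within a comparison**
- Both nulls true, independent: 1 − 0.975² = 4.9% under either rule.
- Only morbidity truly improves, independent: the false-positive chance on SF-36 is 2.5% under Bonferroni. Under Holm it is 2.5% + 0.9155 × 2.5% = 4.8%. It cannot exceed 5%.

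**The case against.** Nothing in the protocol is wrong here. Sections 5.7 and 5.10.4.6 agree, the rule is simple and common, and each outcome has the power promised for it. That stands, and it limits the point to an efficiency suggestion. A reader might infer that the trial is underpowered because 85% is below 90%. The document does not support this: section 5.7 applies the 90% to each outcome separately and claims no joint power.

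The six-point figure also depends on the measure chosen. It is the chance of confirming both outcomes when both full effects are true. Success on at least one is unchanged, and when only one outcome truly responds Holm gives it almost nothing extra. A reader might take 85% to 91% as an unconditional property of the trial. It is not. It assumes independence, the planned effects and 1146 patients in three equal arms, whereas section 5.12 suspends Arm A and leaves the size of comparison a) uncertain.

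The extra power has a cost in error. With one true effect, the false-positive chance on the other outcome nearly doubles. Across comparisons a) and b), which share a control arm and are not adjusted for each other, the chance of at least one such false claim rises from about 4.6% to about 8.6% (simulation, correlation 0.5 from the shared control). This must be disclosed. It does not breach the plan, which controls error at 5% per comparison and accepts separate questions.

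Finally, Bonferroni decisions match 97.5% confidence intervals exactly, and Holm decisions do not. Preferring that match is a defensible choice.

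**Conclusion.** The fixed split is valid and consistent with the sample size. Holm's test would improve on it at the same 5% familywise error per comparison and needs no assumption about correlation to be valid. Under the planned effects and 1146 randomised 1:1:1, it adds about 4 to 7 points to the chance of confirming both outcomes, about 3 points to each, and nothing to the chance of at least one. The direction of the gain does not depend on arm sizes, but the percentages do. This is a worthwhile, low-cost refinement of modest weight; the primary analysis is sound without it.

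**What to change.** In 5.10.4.6, for comparisons a) and b) only, replace the fixed rule with: *Within each comparison the smaller of the two primary p-values is tested at 2.5%; if significant, the larger is tested at 5% (Holm).* Leave the sample size unchanged, since planning at 2.5% is then slightly conservative. Report 97.5% confidence intervals.

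State these limits alongside it:
- An outcome declared at the 5% step may have a 97.5% interval that includes no effect.
- When only one outcome truly improves, the false-positive chance on the other can rise from 2.5% to at most 5%.
- A 30-day result reported before the 12-month SF-36 can be declared only at 2.5% at that time, as under the current rule.

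The cost is a protocol amendment. Section 6.3 gives changes to analyses as an example of a substantial one, so ethics submission and notice to sites are required. It must be made before unblinded outcome data are seen. No extra patients, visits or data are needed.
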